7.4.4. Duration of Response

Duration of response will be assessed with RECIST v1.1 and mRECIST v1.1 criteria.

Censoring of DOR will follow the same algorithm as the censoring of PFS. Kaplan-Meier curves for DOR will be presented by cohort-specific tumor types. The KM estimate of median DOR will be presented with its 95% CI. The 95% CI will be calculated using Brookmeyer and

Crowley's method ([Brookmeyer and Crowley 1982](#)). A swim plot for DOR will be generated under both RECIST v1.1 and mRECIST v1.1 criteria.

7.4.4.1. Duration of Response by RECIST v1.1

Under RECIST v1.1, for objective responders, DOR is defined as the time from the first overall response contributing to an objective response (CR or PR) to the earlier of the subject's death from any cause or first assessment of PD.

7.4.4.2. Duration of Response by mRECIST v1.1

Under mRECIST v1.1, for objective responders, DOR is the time from the first overall response contributing to an objective response (CR or PR) to the earlier of the subject's death from any cause or first confirmed assessment of PD. Note that the criteria for the assessment of PD in DOR are the same with ORR, which are presented in [Section 7.4.2.2](#).

7.4.5. Duration of Disease Control

Duration of disease control (CR, PR, and SD) is defined as the time from the first report of SD or better until disease progression or death from any cause, if occurring sooner than progression, as determined by investigator assessment of radiographic disease per RECIST v1.1 and mRECIST v1.1. Note that the criteria for the assessment of PD in duration of disease control are the same with ORR, which are presented in [Section 7.4.2.2](#).

The duration of disease control will be estimated with 95% CIs overall and by treatment group. Confidence intervals will be calculated based on the exact method for binomial distributions. Swim plots for duration of disease control will be generated separately for RECIST v1.1 and mRECIST v1.1 criteria.

Subjects who do not have sufficient baseline or on-study response assessment information to be adequately assessed for response status will be included in the denominators in the calculation of rate of disease control.

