3.3. Control of Type I Error

All statistical analyses are exploratory in nature. Unless otherwise specified, all CIs provided will be at the 95% confidence level.

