7.4.2.1. Objective Response Rate by RECIST v1.1

Under RECIST v1.1, the best overall response is determined on subject level using the highest overall response achieved postbaseline before and including the first PD, in the order of CR, PR, SD, PD, and NE. Responses of CR, PR, or SD after the first assessment of PD will not be considered. In the case of SD, measurements must meet the SD criteria at least after the date of first dose at a minimum of 49 (56-57) days. Subjects who fail to meet this criterion will have best overall response of PD if the next available assessment indicated PD or NE if there is no additional assessment available.

For subjects with measurable disease at baseline, the RECIST v1.1 assessment criteria presented in [Table 3](#) can be used to determine the overall disease status at a given timepoint based on the target lesion, nontarget lesion, and new lesion assessment.

Table 3: RECIST Evaluation Criteria for Overall Response: Measurable Disease at Baseline

Target Lesions	Nontarget Lesions	New Lesions	Overall Response
CR	CR	No	CR
CR	Non-CR/non-PD	No	PR
CR	NE	No	PR
PR	Non-PD or NE	No	PR
SD	Non-PD or NE	No	SD
Not all evaluated	Non-PD	No	NE
PD	Any	Yes or No	PD
Any	PD	Yes or No	PD
Any	Any	Yes	PD

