7.4.8. Progression-Free Survival

Progression-free survival is defined as the length of time between the baseline visit (Day 1) and the earlier of death or PD as assessed by RECIST v1.1 and mRECIST v1.1. Date of death will be determined using the Death Report CRF.

Censoring for PFS will follow the algorithm outlined in [Table 5](#), which is based on the FDA Guidance for Industry: Clinical Trial Endpoints for the Approval of Cancer Drugs and Biologics ([FDA 2007](#)).

Kaplan-Meier curves for PFS will be presented by cohort-specific tumor types. The KM estimate of median PFS will be presented with its 95% CI. The 95% CI will be calculated using the Brookmeyer and Crowley's method ([Brookmeyer and Crowley 1982](#)).

Table 5: Evaluation and Censoring of Progression-Free Survival

Situation	Outcome	Date of Progression or Censoring
No baseline tumor assessments	Censored	Date of Day 1
No valid postbaseline response assessments	Censored	Date of Day 1
Progression documented between scheduled response assessments	Progressed	Date of first overall response of PD
No progression	Censored	Date of last valid radiologic assessment (not NE and not missing)
Study discontinuation for undocumented progression	Censored	Date of last valid radiologic assessment (not NE and not missing)
Study discontinuation for toxicity or other reason	Censored	Date of last valid radiologic assessment (not NE and not missing)
New anticancer treatment started	Censored	Date of last valid radiologic assessment (not NE and not missing) on/before starting a new anticancer treatment
Death before first progressive response assessment	Progressed	Date of death
Death between adequate response assessments	Progressed	Date of death
Death or progression after more than 1 missed assessments	Censored	Date of last valid radiologic assessment (not NE and not missing) before death

NE = not evaluable.

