7.4.8.2.1. Confirmation of Progression per mRECIST v1.1

Under mRECIST v1.1, the assessment of PD will be confirmed by a second consecutive assessment at least 4 weeks but no later than 6 weeks apart with the option for continuing treatment while awaiting radiologic confirmation of progression ([Table 4](#)).

- If after the first unconfirmed PD, there is an EOT/EOS or a new treatment is started, this unconfirmed PD will be counted as a confirmed PD, and DOR will be defined as the time from the first overall response (CR or PR) to this PD, or death from any cause if occurring sooner than the PD.
- If a second PD occurs after the first unconfirmed PD, the first unconfirmed PD will be counted as a confirmed PD, and DOR will be defined as the time from the first overall response (CR or PR) to the first PD, or death from any cause if occurring sooner than the confirmed PD.
- If a CR, PR, SD, or NE occurs after the first unconfirmed PD, the unconfirmed PD will not be counted as a PD. If there is no further PD assessment, DOR will be censored.

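### Duration of disease control, a time-to-event endpoint, is given an exact binomial confidence interval, with no type of median and no censoring rule stated

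*SAP*

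**What the plan says.** SAP 7.4.5 measures duration of disease control from the first report of SD or better to progression or death, as do Protocol 2.2.2 and SAP 2.3.2. It then states: "The duration of disease control will be estimated with 95% CIs overall and by treatment group". The next sentence names the method: "Confidence intervals will be calculated based on the exact method for binomial distributions". The section ends with a rule for a different quantity, under which subjects without adequate response data are "included in the denominators in the calculation of rate of disease control".

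In SAP Appendix A, the shells for Tables 2.1.1, 2.1.2, 2.2.1 and 2.2.2 each have a row for the median duration of disease control, with the word Range in brackets and a pointer to footnote [4]. That footnote repeats the exact binomial method. The 95% level comes from 7.4.5 and SAP 3.3, not from the footnote.

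For duration of response (DOR), SAP 7.4.4 specifies Kaplan-Meier curves and median, a Brookmeyer-Crowley 95% CI, and this rule: "Censoring of DOR will follow the same algorithm as the censoring of PFS". Footnote [3] attaches the Brookmeyer-Crowley method to the DOR row in the same four shells.

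**The concern.** The method does not fit the quantity. A binomial interval is computed from a count and a denominator and has no time unit, so it cannot bound a median in days. Read literally, a row that reports a duration would carry a percentage interval. The row label adds to the confusion, because it promises a range while its footnote describes a confidence interval.

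Two further choices are open. The SAP text names no summary statistic. The shells say median, without saying whether it comes from Kaplan-Meier or from the observed times. No censoring rule covers the endpoint either, so a subject still controlled at the data cutoff, or one who starts a new anticancer treatment, has no defined end date. If these choices are left to the programmer, the reported median could depend on decisions made after the data have been seen.

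**Working it through.** The plan states no figure for this endpoint, so there is nothing to reproduce. The check has three parts.

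**1. What the named method returns.** The exact (Clopper-Pearson) 95% interval for x of n is

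lower = Beta quantile at 0.025 with parameters (x, n − x + 1); upper = Beta quantile at 0.975 with parameters (x + 1, n − x).

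The values of n are the planned Part 2 cohort sizes, 17 in full and 9 at Stage 1. The counts x are assumed.

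| x / n | Proportion | Exact 95% CI |
|---|---|---|
| 6 / 17 | 35.3% | 14.2% to 61.7% |
| 12 / 17 | 70.6% | 44.0% to 89.7% |
| 15 / 17 | 88.2% | 63.6% to 98.5% |
| 6 / 9 | 66.7% | 29.9% to 92.5% |

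For 12 / 17 the quantiles come from Beta(12, 6) and Beta(13, 5). No duration enters the formula, so setting all 12 durations to 8 weeks or all to 40 weeks leaves 44.0% to 89.7% unchanged.

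**2. Whether a rule elsewhere fills the gap.**

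- SAP 7.4.8 says "Censoring for PFS will follow the algorithm outlined in" Table 5. That rule is for PFS.
- SAP 7.4.4 extends it to DOR and to nothing else.
- SAP 7.4.8.2.1, on a PD that is not confirmed, says: "If there is no further PD assessment, DOR will be censored". Again only DOR is named.
- SAP 7.4.5 cross-refers to 7.4.2.2, whose Table 4 decides whether a PD counts as an event. It gives no censoring date for a subject without an event.
- Protocol 9.4.1.2 assigns Kaplan-Meier to PFS and DOR only, and the planned Kaplan-Meier figures in SAP Appendix A cover the same two endpoints.

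**3. Where the binomial method would fit.** Protocol 9.4.1.2 plans a summary of the proportion with disease control (CR + PR + SD), and SAP 7.4.5 sets its denominator. An exact binomial interval suits that rate. The rate has no row in the four shells and no table of its own in the planned list, so the method is attached to the wrong quantity and the right quantity has no output.

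**The case against.** The strongest reply is that this is a drafting slip. The binomial sentence was probably meant for the rate. The shells are marked draft and contain other misplaced footnotes: in Table 2.1.1, for example, footnote [2] sits on the responder row but defines DOR. Appendix A calls the shells a guideline that can be changed without an SAP amendment if the nature of the analysis is unaffected. That is a fair account of the likely origin, but the sentence also stands in the body of the SAP, where it names the duration.

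A second reply is that one binomial interval does apply to a median, the order-statistic interval. For n = 17 it runs from the 5th to the 13th ordered value, with coverage 1 − 2 × P(Bin(17, 0.5) ≤ 4) = 95.1%. Neither document mentions it, and it needs uncensored times. In a simulation with 8,000 runs per setting (assumed: 17 durations, exponential, true median 16 weeks, independent exponential censoring) the results were:

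| Censored | Order-statistic coverage | Brookmeyer-Crowley coverage | Plain sample median (weeks) | Kaplan-Meier median (weeks) |
|---|---|---|---|---|
| 0% | 95.5% | 97.1% | 16.0 | 16.0 |
| 30% | 81.9% | 95.6% | 11.3 | 16.1 |
| 50% | 43.9% | 95.1% | 8.0 | 16.2 |

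This reading therefore does not rescue the text, and the table shows why the type of median matters.

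A third reply is that the Protocol synopsis promises only descriptive statistics for other efficacy variables, so an observed median with its range may have been intended. That is possible, and it would explain the row label. It does not override the SAP's explicit commitment to a 95% CI. It does mean that Kaplan-Meier here is a choice by analogy with DOR and goes beyond what Protocol 9.4.1.2 lists.

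**Conclusion.** The concern holds. As written, SAP 7.4.5 and footnote [4] in four shells assign an interval for a proportion to a time-to-event endpoint. The type of median and the censoring rule are not stated anywhere in either document. The mismatch itself rests on no assumption. The illustrative intervals rest on assumed counts, and the simulated coverage on an assumed duration distribution and censoring pattern.

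The severity is minor. The effect is confined to the reporting of one secondary endpoint, and SAP 3.3 says: "All statistical analyses are exploratory in nature". The Simon decision rules, the sample size and the safety rules do not depend on it.

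**What to change.** Replace the two estimation sentences in SAP 7.4.5 with text to this effect:

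> Duration of disease control will be estimated by Kaplan-Meier in subjects with at least one report of SD or better before progression, by dose group in Part 1 and by tumor type in Part 2, with censoring as in Table 5. The median will be shown with its Brookmeyer-Crowley 95% CI. The disease control rate (CR + PR + SD) in the FAS will be shown with an exact binomial 95% CI.

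Keep the closing denominator paragraph for the rate. Presenting Part 2 by tumor type matches the columns of Tables 2.1.2 and 2.2.2; an overall estimate, if still wanted, needs its own column.

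The text should also say which SD definition each quantity uses. The wording above keeps the start point of 7.4.5 and does not bring in the condition in SAP 7.4.2.1 that "measurements must meet the SD criteria at least after the date of first dose at a minimum of 49 (56-57) days". That condition belongs to best overall response under RECIST v1.1. If the rate is based on best overall response, a subject with one early SD could enter the duration analysis without counting in the rate, and a footnote should say so.

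In the four shells, make the row label and footnote [4] agree on a Kaplan-Meier median with its Brookmeyer-Crowley 95% CI; the range may stay as an addition. Add a disease control rate row that carries the binomial footnote.

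The cost is SAP wording plus one footnote, one label and one added row in each of four shells. The DOR code can be reused. Study conduct and data collection do not change.

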7.4.6. Largest Percentage Reduction in Sum of Diameters of Target Lesions

For each subject in the FAS population with target lesions at baseline, target lesion sizes will be measured by sum of diameters. The best percentage change from baseline, defined as the largest decrease in target lesion size for each subject, will be summarized descriptively, and a waterfall plot of the best percentage change will be generated.

Per RECIST criteria, target lesions considered "too small to measure" will be assigned a default value of 5 mm for purposes of this analysis. Likewise, target lesions identified as "not present" at postbaseline assessments will be assigned 0 mm for this analysis. In the event a target lesion is unaccounted for in a particular postbaseline timepoint (ie, assessment missing or NE), then the overall sum of diameters for target lesions will not be evaluable for that postbaseline timepoint.

7.4.7. Percentage Change in Sum of Diameters of Target Lesions Over Time

For each subject in the FAS population with target lesions at baseline, target lesion sizes will be measured by sum of diameters. The percentage change in sum of diameter of target lesions over time will be listed and a spider plot will be generated.

7.4.8. Progression-Free Survival

Progression-free survival is defined as the length of time between the baseline visit (Day 1) and the earlier of death or PD as assessed by RECIST v1.1 and mRECIST v1.1. Date of death will be determined using the Death Report CRF.

Censoring for PFS will follow the algorithm outlined in [Table 5](#), which is based on the FDA Guidance for Industry: Clinical Trial Endpoints for the Approval of Cancer Drugs and Biologics ([FDA 2007](#)).

Kaplan-Meier curves for PFS will be presented by cohort-specific tumor types. The KM estimate of median PFS will be presented with its 95% CI. The 95% CI will be calculated using the Brookmeyer and Crowley's method ([Brookmeyer and Crowley 1982](#)).

Table 5: Evaluation and Censoring of Progression-Free Survival

Situation	Outcome	Date of Progression or Censoring
No baseline tumor assessments	Censored	Date of Day 1
No valid postbaseline response assessments	Censored	Date of Day 1
Progression documented between scheduled response assessments	Progressed	Date of first overall response of PD
No progression	Censored	Date of last valid radiologic assessment (not NE and not missing)
Study discontinuation for undocumented progression	Censored	Date of last valid radiologic assessment (not NE and not missing)
Study discontinuation for toxicity or other reason	Censored	Date of last valid radiologic assessment (not NE and not missing)
New anticancer treatment started	Censored	Date of last valid radiologic assessment (not NE and not missing) on/before starting a new anticancer treatment
Death before first progressive response assessment	Progressed	Date of death
Death between adequate response assessments	Progressed	Date of death
Death or progression after more than 1 missed assessments	Censored	Date of last valid radiologic assessment (not NE and not missing) before death

NE = not evaluable.

7.4.8.1. Progression-Free Survival by RECIST v1.1

Under RECIST v1.1, PFS is defined as the length of time between the baseline visit (Day 1) and the earlier of death or first assessment of PD as assessed by RECIST v1.1.

7.4.8.2. Progression-Free Survival by mRECIST v1.1

Under mRECIST v1.1, PFS is defined as the length of time between the baseline visit (Day 1) and the earlier of death or first overall confirmed assessment of PD (as described in [Section 7.4.2.2](#)).

7.4.8.2.1. Confirmation of Progression per mRECIST v1.1

Under mRECIST v1.1, the assessment of PD will be confirmed by a second consecutive assessment at least 4 weeks but no later than 6 weeks apart with the option for continuing treatment while awaiting radiologic confirmation of progression ([Table 4](#)).

- If after the first unconfirmed PD, there is an EOT/EOS or a new treatment is started, this unconfirmed PD will be counted as a confirmed PD, and DOR will be defined as the time from the first overall response (CR or PR) to this PD, or death from any cause if occurring sooner than the PD.
- If a second PD occurs after the first unconfirmed PD, the first unconfirmed PD will be counted as a confirmed PD, and DOR will be defined as the time from the first overall response (CR or PR) to the first PD, or death from any cause if occurring sooner than the confirmed PD.
- If a CR, PR, SD, or NE occurs after the first unconfirmed PD, the unconfirmed PD will not be counted as a PD. If there is no further PD assessment, DOR will be censored.

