7.4.2.2. Objective Response Rate by mRECIST v1.1

The mRECIST v1.1 instrument was adapted from RECIST v1.1 to include criteria that accounts for new lesions that can occur in immuno-oncology subjects before the occurrence of an SD, PR, or CR. Under mRECIST v1.1, if radiologic imaging shows PD, tumor assessment should be

repeated at a minimum of 4 weeks but not more than 6 weeks later to confirm the progression. If there is no second PD tumor assessment in the 4- to 6-week follow-up time, the PD will be defined as unconfirmed. [Table 4](#) lists the scenarios that can occur after an unconfirmed PD in at least 4 weeks and no more than 6 weeks, and provides rules for determining whether or not the unconfirmed PD will be counted as an event in the corresponding scenario.

Table 4: Rules for Determining PD Event Status After an Unconfirmed PD

Event Occurring After Unconfirmed PD in the Confirmation Window (4-6 Weeks)	PD Event Status
Subject had EOS/EOT or started new anticancer therapy.	PD will be confirmed as a PD.
Subject had a confirmed PD.	PD will be confirmed as a PD.
Subject had an CR, PR, SD, or NE.	PD will not be considered as a PD and counted as corresponding CR, PR, SD, or NE for the second timepoint only.

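### The SAP lets a not-evaluable repeat scan cancel a documented mRECIST progression, and gives no single event status to in-window end of treatment, palliative radiation or death before the first scan

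*SAP*

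**What the plan says.** **NE and confirmation.** Under mRECIST, PFS runs to death or the "first overall confirmed assessment of PD" (SAP 7.4.8.2). SAP 7.4.2.2 states: "If there is no second PD tumor assessment in the 4- to 6-week follow-up time, the PD will be defined as unconfirmed". Table 4 then decides whether such a PD counts. Its first column is headed "Event Occurring After Unconfirmed PD in the Confirmation Window (4-6 Weeks". For a repeat result of CR, PR, SD or NE, the outcome is "PD will not be considered as a PD and counted as corresponding CR, PR, SD, or NE for the second timepoint only". SAP 7.4.8.2.1 repeats the scheme in three bullets, which carry no window of their own:

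1. "there is an EOT/EOS or a new treatment is started, this unconfirmed PD will be counted as a confirmed PD"
2. "If a second PD occurs after the first unconfirmed PD, the first unconfirmed PD will be counted as a confirmed PD"
3. "If a CR, PR, SD, or NE occurs after the first unconfirmed PD, the unconfirmed PD will not be counted as a PD"

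The footnotes of Tables 2.2.1 and 2.2.2 also treat NE like CR, PR and SD. SAP 7.4.4.2 and 7.4.5 apply the 7.4.2.2 criteria to DOR and to duration of disease control.

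**Censoring.** SAP Table 5 governs PFS, and "Censoring of DOR will follow the same algorithm as the censoring of PFS". It censors at the last valid radiologic assessment, and NE does not qualify as valid. One row censors at Day 1 a subject with no valid postbaseline assessment. Another counts as an event, at the date of death, a death that precedes the first progressive assessment. No order of rows is given.

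**Radiation.** Protocol 5.6.3 treats palliative radiation as clinical progression for PFS. Protocol 2.2.2 and SAP 2.3.2 define PFS by radiographic progression or death. Table 5 does not mention radiation.

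**The concern.** The NE rule turns absence of information into a finding of no progression. The protocol's own account of non-confirmation is narrower. Table 12 names only SD, PR or CR on the repeat scan, and Protocol 1.3.3.1.1 asks for positive findings: tumor burden back below the progression threshold, and stable or improved lesions. The SAP is also uneven within itself. A PD with no repeat scan that is followed by end of treatment counts as an event, yet a PD with an uninformative repeat scan is cancelled.

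The other gaps are of one kind: a subject's history satisfies two rules with different answers, or no rule at all. Two programmers who both follow the plan can then give the same subject a different event status. With 9 or 17 subjects per cohort, a single reclassification shows in the reported estimate.

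**Working it through.** The documents state no event count, median or power for PFS or DOR, so there is no planned figure to reproduce. I applied each rule literally to test sequences, then used Kaplan-Meier, S(t) = product of (1 - d/n) over event times. All cohort patterns below are assumptions; only the Week 8 and Week 16 scan times and the cohort sizes of 9 and 17 come from the documents.

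**Rules set side by side**

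| Sequence | Rule giving an event | Rule giving no event |
|---|---|---|
| PD Week 8, NE Week 13, EOT Week 14 (5 and 6 weeks after the PD) | Table 4 row 1, bullet 1: event at Week 8 | Table 4 row 3, bullet 3: PD not counted |
| Palliative radiation Week 12, no PD on scan | Protocol 5.6.3: progression | SAP Table 5: no row; ignored, or censored if read as new anticancer treatment |
| Death on Day 40, no scan yet (first scan is due at Week 8) | PFS definition in SAP 7.4.8 and the early-death row: event at Day 40 | Row for no valid postbaseline assessment: censored at Day 1 |

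In the first sequence both later events lie inside the window, so the window does not settle it. An SD, PR or CR in place of the NE gives the same clash.

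**One PD at Week 8 followed by NE**

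- N = 17, 8 PDs at Week 8. PD counted: 1 - 8/17 = 9/17 = 52.9%. PD voided and the subject censored at the Week 8 scan: 1 - 7/17 = 10/17 = 58.8%. The step is 1/17 = 5.9 points.
- N = 9, 4 PDs at Week 8: 5/9 = 55.6% against 6/9 = 66.7%, a step of 11.1 points.

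**One death before any scan, half of the others PD at Week 8**

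- N = 17. Event: 16/17 x 8/16 = 8/17 = 47.1%. Censored at Day 1: 8/16 = 50.0%.
- N = 9. Event: 8/9 x 4/8 = 4/9 = 44.4%. Censored at Day 1: 4/8 = 50.0%.

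**One subject irradiated at Week 12** (N = 17, 9 progression-free after Week 8, 4 of the other 8 PD at Week 16)

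- Event at Week 12: 9/17 x 8/9 x 4/8 = 4/17 = 23.5% at Week 16.
- Censored at the Week 8 scan: 9/17 x 4/8 = 26.5%.
- Ignored, with no PD at Week 16: 9/17 x 5/9 = 5/17 = 29.4%.

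**The case against.** The best defence of the NE rule is that it is deliberate. It appears consistently in Table 4, in 7.4.8.2.1 and in two table footnotes. Where progression must be confirmed, an NE scan does not confirm it. Table 5's exclusion of NE sets a censoring date and does not strictly contradict Table 4. RECIST v1.1 PFS and DOR, which use the first PD, are reported alongside. It stands that the rule is no slip and that the RECIST v1.1 results escape it. But failing to confirm is not the same as refuting: the PD should stay open, and the protocol does not list NE among the results that reverse it. The RECIST v1.1 PFS results still share the radiation and early-death gaps.

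On early death, the definition and the more specific row agree on an event, so the intention is fairly clear. The Day 1 row still says otherwise, and no order overrides it.

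A reader might also infer that PD, then NE, then a PD beyond six weeks has two competing dates, because bullet 2 states no limit. The documents largely close that off. The lead-in to the bullets asks for a second consecutive assessment at 4 to 6 weeks, Table 4 repeats the window, and Protocol 7.7.1 dates an unconfirmed progression to a later PD that is itself confirmed. What remains is that the bullets should state the window. An NE and a second PD both inside the window would need an extra scan beyond the single scheduled repeat, so I do not rely on that case.

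**Conclusion.** The concern holds in four parts. For mRECIST PFS, DOR and duration of disease control, (a) an NE repeat scan wrongly cancels a documented PD, and (b) NE, SD, PR or CR together with end of treatment, end of study or new therapy in the window has two answers. For PFS under both criteria, (c) palliative radiation is progression in one protocol section and absent from the endpoint definition and from Table 5, and (d) Day 1 censoring of a death before any scan contradicts the definition in the same SAP section.

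The illustrated effect of one subject is about 3 to 6 points of PFS in a cohort of 17 and about 6 to 11 points in a cohort of 9. That rests on the assumed patterns. The documents give no rate of NE repeat scans, radiation or early deaths, so the real size is unknown. The endpoints are secondary (SAP 7.1) and the analyses exploratory (SAP 3.3). This should be corrected, but it does not undermine the design.

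Two further inferences are not supported. One is that the cross-reference in SAP 7.4.5 leaves open which criterion applies: footnote 4 of Tables 2.1.1 and 2.1.2 specifies RECIST v1.1, and footnote 4 of Tables 2.2.1 and 2.2.2 specifies mRECIST. The other is that the Simon decision is insulated from the NE rule. Protocol 9.4.1.1 judges Part 2 response by mRECIST, and the footnotes of Table 2.2.2 run best response up to the first confirmed PD. After PD, NE, EOT and a later PR, keeping or voiding the PD could change responder status. The documents do not show how often that would happen.

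**What to change.** - **NE rule.** Remove NE from the cancelling row of Table 4, from bullet 3 of 7.4.8.2.1 and from the footnotes of Tables 2.2.1 and 2.2.2. An NE repeat then leaves the PD unresolved until the next evaluable scan, EOT/EOS or new therapy. State that EOT/EOS or new therapy after PD then NE keeps the first PD as an event. Say how a PD still unresolved at data cutoff is counted.
- **Window and order.** State the 4-6 week window and the order of precedence for all three bullets, including SD, PR or CR followed by EOT inside the window. Date a PD found after six weeks consistently with Protocol 7.7.1.
- **Early death.** Limit the Day 1 censoring row of Table 5 to subjects with no valid postbaseline assessment who have not died. State its order against the row that censors a death or progression following more than one missed assessment.
- **Radiation.** Reconcile Protocol 5.6.3 with the radiographic PFS definition as an analysis rule, add the matching Table 5 row, and report the other reading as a sensitivity analysis.

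The cost is SAP wording, programming and at most one extra table. Reported PFS and DOR may change slightly.
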